While the long-term health effects of e-cigarettes are still unclear, studies examining proximal biomarkers of health indicate that e-cig users are exposed to many cardiovascular and pulmonary toxicants, including carcinogens, such as carbonyls, furans, reactive oxygen species, and heavy metals^{6,7}. Early evidence indicates that e-cig users experience adverse health effects, including increased oxidative stress, respiratory and mucosal inflammation, arterial stiffness and altered hemodynamics and platelet activity⁸. Moreover, use of nicotine by youth can adversely affect attention, learning, and memory, as well as lead to increased impulsivity. Taken together these data suggest that sustained e-cig use will likely have notable adverse health effects⁹. Since their introduction in 2015, to our knowledge, no studies have examined the toxicological and physiological effects of NSB device use, nor the impact of nicotine form. Previous research has largely focused on free-base nicotine devices, with only a few focusing on pulmonary and cardiovascular effects.

The youth vaping epidemic in the U.S. is drawing serious concern from parents, schools, health officials and regulators. There is now a wave of support and a need to create effective e-cig policies and regulations to prevent further proliferation of youth e-cig use. One of the most effective policies may be to create a product standard for nicotine to reduce the palatability and abuse liability of e-cigs for youth;

Evaluating E-Cigarette Nicotine Form, Concentration, and Flavors among Youth

however, strong scientific evidence is needed for the FDA to impose such regulations. The proposed project will begin to address this need.

A. Specific Aims

Utilizing a human laboratory design, we will examine the influence of nicotine form and concentration, and e-liquid flavor on youth vaping behavior, nicotine uptake, abuse liability, toxicant exposure, and acute cardiovascular and pulmonary effects. H1a: Nicotine salt (vs. free-base) and menthol flavored e-liquids (vs. tobacco flavored) will result in puffs of longer duration and higher flow rate, and a greater total inhaled aerosol volume, and H1b: demonstrate greater nicotine uptake, abuse liability, and adverse cardiovascular and pulmonary effects. H1c: High concentration, free-base nicotine (vs. salt nicotine) will result in puffs of shorter duration, lower flow rate, less volume, and lower abuse liability.

B. Significance

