Laboratory Spirometry (SpiroLab)	X	X
Airway Inflammation (NIOX VERO)	X	X
Airway Reactivity (TremoFlo)	X	X
Cardiovascular Measures		
Vascular Reactivity (Vicorder or similar)	X	X
Blood Pressure	X	X
Heart Rate	X	X
Markers of endothelial dependent and independent function		
B-mode ultrasound (Vicorder or similar)	X	X
Arterial stiffness		
Pulse wave velocity and analysis (Vicorder or similar)	X	X

Evaluating E-Cigarette Nicotine Form, Concentration, and Flavors among Youth

E. Statistical Methods

Generalized linear mixed models will be employed to identify associations of nicotine form, nicotine concentration, and flavoring with various outcome measures (e.g., plasma nicotine, spirometry, flow-mediated dilation). Models will include relevant covariates (e.g., gender), a random effect for participant, main effects for nicotine form and concentration, and the interaction between nicotine form and concentration and nicotine form and flavor. Because of multiple measurements tested, we will assume a significance threshold corresponding to one expected false discovery per 100 tests ($p=0.01$).

i. Power Analysis

This study, for each of the main effects and $\alpha = 0.01$, achieves 80% power to detect an effect size of 0.5 standard deviations of the paired differences. For interaction effects, we will estimate 80% power (effect size 0.5 SD) to distinguish between any two of the interaction groups (e.g., free base/low nic, free base/high nic), while correcting for the pairwise tests ($p=0.01/6=0.0017$). Carryover and period effects will also be examined.

ii. Data Analytic Plan

Because product sampling will be randomized using a Latin Square, a fixed effect for session and a random effect for sequence will be included in all analyses.

iii. Missing Data

While we will make every effort to minimize the missing data for this study, missing data can arise due to various reasons. Violation of missing complete at random (MCAR) will be checked by evaluating whether any covariates are associated with missing data. If so, these covariates will be subsequently included and controlled for in the GLMM model. Our primary analysis will use mixed models which assumes Missing At Random (MAR) to deal with the missing data problem. In addition, sensitivity analyses will also be conducted using results from multiple imputation and complete cases strategies.

F. Gender/Minority/Pediatric Inclusion for Research

i. Inclusion of Women and Minorities

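### The model's term list gives flavor no main effect and no overall menthol-versus-tobacco contrast, although H1a and H1b predict that difference

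*Combined protocol and SAP*

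**What the plan says.** - **Hypotheses (A. Specific Aims).** H1a states that "Nicotine salt (vs. free-base) and menthol flavored e-liquids (vs. tobacco flavored) will result in puffs of longer duration and higher flow rate", along with greater inhaled volume. H1b says that the same products will "demonstrate greater nicotine uptake, abuse liability, and adverse cardiovascular and pulmonary effects". Neither limits the flavor comparison to one nicotine form or concentration.
- **Design (D.ii Study Procedures).** Eight liquids cross form, concentration and flavor within each participant.
- **Purpose of the models (E. Statistical Methods).** They are meant to "identify associations of nicotine form, nicotine concentration, and flavoring with various outcome measures".
- **Model terms (same paragraph).** Besides covariates and a participant random effect, the terms are "main effects for nicotine form and concentration, and the interaction between nicotine form and concentration and nicotine form and flavor". The general threshold is p=0.01.
- **Power (E.i).** At alpha 0.01 the plan claims, "for each of the main effects", "80% power to detect an effect size of 0.5 standard deviations of the paired differences". For interactions it claims 80% power to "distinguish between any two of the interaction groups (e.g., free base/low nic, free base/high nic), while correcting for the pairwise tests", at 0.01/6=0.0017.
- **Further model terms (E.ii).** The plan adds only that "a fixed effect for session and a random effect for sequence will be included in all analyses".

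**The concern.** Flavor is one of three crossed factors and is part of two hypotheses, yet the main effects cover only form and concentration. Nothing in Section E, E.i or E.ii names a flavor main effect or a menthol-minus-tobacco contrast averaged over form and concentration. The 0.01 threshold therefore has no flavor test to attach to.

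Three tests could be taken to decide the flavor hypothesis: the overall 1-df contrast at 0.01, the listed form-by-flavor term at 0.01, and within-form pairs at 0.0017. They answer different questions and can disagree. Table 1 lists many outcomes, and the plan chose 0.01 because of them. Leaving this choice open until the data are in view weakens that protection.

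**Working it through.** **Inputs from the documents.** 60 completers; 8 liquids each; effect size 0.5 SD; alpha 0.01 for main effects and 0.01/6 for pairs.

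**Assumptions.** The documents give no variances and do not state sidedness. I assume two-sided tests, complete data, independent residuals of equal SD σ after the participant effect is removed, and no session or sequence effects. The percentages are therefore illustrative.

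**Step 1: the plan's own figures.**
- Four cells of a 2×2 interaction give 6 pairs, and 0.01/6 = 0.00167, so 0.0017 reproduces.
- For a main effect, a paired t test with n=60 and d=0.5 at 0.01 has 88.2% power, so the stated 80% is met as a minimum.

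**Step 2: what the listed terms can estimate.** Over the eight cells, class coding of the listed terms gives a design matrix of rank 6. Adding a flavor main effect leaves it at 6. The listed form-by-flavor term then carries flavor within each form (2 df), and the average of those two effects is the overall flavor contrast.

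**Step 3: overall contrast against the listed term.**
- The contrast is the mean of 4 menthol sessions minus the mean of 4 tobacco sessions. Its SD per participant is σ√(1/4 + 1/4) = 0.707σ.
- A uniform effect of 0.5 SD of that difference is 0.5 × 0.707σ = 0.354σ.
- Noncentrality is 60 × 0.5² = 15. Residual df are 480 − 60 − 5 = 415.
- 1-df contrast at 0.01 (noncentral F): **90.0%** power (simulated, 20,000 runs: 89.7%).
- 2-df listed term at 0.01: **83.3%** (simulated: 82.9%).

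**Step 4: equal and opposite effects.** Let flavor effects be +0.354σ in one form and −0.354σ in the other. Each form contributes 60 × 0.354² = 7.5, so the 2-df noncentrality is again 15. The listed term rejects in about **83%** of trials. The overall effect is zero, and the 1-df contrast rejects in about 1%.

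**Step 5: within-form pairs at 0.01/6.** Only 2 of the 6 form-by-flavor pairs compare menthol with tobacco within a form. Each is a mean of 2 sessions minus a mean of 2, with SD σ√(1/2 + 1/2) = σ. The plan does not say which SD its 0.5 refers to, so both readings are shown. Where two figures are given, the first is a paired t test on 59 df and the second uses the model's 415 df.

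| 0.5 SD refers to | Noncentrality | Power per pair | Both forms detected | Overall contrast at 0.01 (415 df) |
|---|---|---|---|---|
| overall paired difference | 0.354 × √60 = 2.74 | 30% / 34% | 9% / 11% | 90.0% |
| within-form paired difference | 0.5 × √60 = 3.87 | 71% / 76% | 51% / 58% | 99.8% |

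The figures for both forms are the squares of the per-pair power, which treats the two forms as independent. If the two within-form differences were almost perfectly correlated, the two readings would converge, and per-pair and joint power would both be about 71% by paired t test.

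**The case against.** The strongest reply is that this is a slip with little consequence. The opening sentence of Section E names flavoring, the list of terms is not said to be exhaustive, and E.i speaks of each main effect. Under class coding the overall contrast can be computed from the model as listed. The 2-df test still exceeds the plan's 80% target, and its fitted within-form effects carry signs that a reader can inspect. Most of this stands, and it limits the point to prespecification. It does not supply the missing contrast, and reading the signs after a 2-df rejection is not a test of an overall menthol effect.

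A second reply is that the pairwise clause in E.i covers flavor. It can be read that way, but it sits under power, its only example is form by concentration, and two within-form comparisons at a stricter threshold are not the overall comparison.

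Three stronger readings are tempting, and the documents do not support them:
- **Flavor cannot be estimated, or would go untested altogether.** Step 2 shows otherwise under class coding. It would need form-by-flavor to be fitted as a numeric product without its parent term, which nothing in the plan suggests.
- **The form effect is compromised.** Under class coding it is not.
- **Relying on the pairs would usually miss a uniform flavor effect in at least one form.** This holds if 0.5 SD refers to the overall paired difference. If it refers to the within-form difference, both forms are detected in 51% to 58% of trials. The plan does not settle which is meant.

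**Conclusion.** The point holds as a gap in prespecification that should be fixed. H1a and H1b state an overall flavor effect; the term list and the power text assign it neither a term, nor a contrast, nor an alpha. The power cost of relying on the listed term is modest, about 83% against 90%. The larger problem is interpretive: that term can reject in about 83% of trials with no overall menthol effect. Within-form pairs are weaker than the overall contrast under either definition of the effect size. The percentages depend on the assumptions listed in the working. The mismatch between hypotheses and term list does not. The design, the data to be collected and the sample size are not in question here.

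**What to change.** In Section E, change the list of terms to: 'main effects for nicotine form, concentration and flavor, and the form-by-concentration and form-by-flavor interactions'.

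Then add a sentence stating that the flavor part of H1a and H1b is tested by the 1-df menthol-minus-tobacco contrast, averaged over form and concentration, at p=0.01, with within-form flavor contrasts reported as follow-up to the interaction.

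If within-form comparisons are the real target, the plan should say so and state that the pairwise clause and its 0.0017 threshold apply to form by flavor.

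The cost is two sentences. Under class coding the model uses no extra degree of freedom (rank 6 either way). No new data and no change to design or sample size are needed.

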Utilizing a within-subjects, factorial design, 60 e-cig users (aged 21-25 years) will complete vaping sessions which will include a standardized, 5-minute, 10-puff vaping bout (30 seconds between each puff) followed by 30 minutes of ad libitum vaping. Prior to session one, participants will be asked to bring their own e-cig device and a full tank/pod to the first visit. In session one, participants will use their own e-cig and e-liquid. After visit 1, participants will take home a study e-cig device and 1 weighed pod pre-filled with study e-liquid (the participant was randomized to at the end of visit 1) to practice (20 puffs per day with the study device and until the participant feels comfortable) using the device before visit 2. Practice use with the study e-cig device and pre-filled pod will be verified based on data downloaded (via eScribe) from the device during visit 2. In the subsequent vape sessions, participants will use a study e-cig held at a constant wattage, and pre-filled with e-liquid of different nicotine form (free-base vs. nicotine salt), concentration (low-1% vs. high-5%), and flavoring (tobacco vs. menthol). There is no known commercial pair of nicotine liquids that differ only by nicotine form. For this study, we will prepare 8 e-liquids that differ by nicotine form, nicotine concentration, and flavor, simulating characteristics of popularly used nicotine liquids^{32,39}. E-liquids will be prepared from pure ($\geq 99\%$) S-(-)-nicotine; protonation and dilution of nicotine will be done using USP grade benzoic acid, and glycerol and propylene glycol, respectively. We will submit an Investigational Tobacco Product application to the U.S. FDA regarding the clinical use of the e-liquids. All sessions will be completed over nine visits for schedule Option A and 5 visits for schedule Option B. Study Schedule A consist of 9 separate visits and 9 separate vaping sessions. Study schedule B will consist of five separate visits (each visit will include up to 2 vaping sessions) each separated by a 3-hour washout period to allow nicotine levels to return to baseline. Each visit will be at least 48 hours apart. Participants will be required to report at least 12 hours abstinent from nicotine before each study visit. Participants will be told that their abstinence will be confirmed at the time of visit via blood plasma nicotine analysis. This is a partial bogus pipeline⁴⁰; 3mL venous blood sample will be collected for later analysis.; those with plasma nicotine levels $>3\text{ng/mL}$ at the time of their visit will be replaced post hoc with another participant. We conservatively estimate replacing 10% of participants. Measures of topography, nicotine uptake, abuse liability, subjective effects, and cardiovascular and pulmonary effects will be collected (see Table 1). Exposure to select toxicants, including nicotine and menthol in total particulate matter, and gas phase carbonyls and volatile organic compounds, will also be estimated post hoc using puff playback machine smoking.

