
1. Recruitment Feasibility and Retention

a) Recruitment

We intend to recruit 130 e-cig users from the community over an 18-month period and have them complete nine study visits (Option A) or five study visits (Option B); therefore, we need 3-4 participants to be recruited and complete study procedures per month.

We are confident our recruitment approach, laboratory facilities, and equipment redundancy will result in a sufficient participant processing rate, given our successful completion of other tobacco-related research of similar design⁴¹. E-cig users will be recruited from advertisements through a variety of media outlets and the internet, including Study Search, as well as community events. Participants from

Evaluating E-Cigarette Nicotine Form, Concentration, and Flavors among Youth

other studies who have agreed to be contacted regarding other study opportunities will also be contacted. Staff from those studies will prepare contact letters/emails and call participants on behalf of this study. Interested participants will be referred to this study for screening. Participants will access the screening questionnaire using a public survey link generated by REDCap. Based on our team's previous studies, we conservatively assume a 20% attrition rate. Thus, we need to recruit 130 participants to have 60 complete the study. Participants who meet the following eligibility criteria will be asked to take part in the study.

Inclusion criteria: 1) a current e-cigarette user (≥ 1 vaping bout per day) for at least the past 3 months , 2) 21-25 years old, 3) willing to abstain from all tobacco and nicotine for at least 12 hours prior to lab sessions, 4) willing to complete nine lab visits/vaping session lasting up to 2 hours each or five lab visits lasting up to 6 hours each (except Visit 1) , 5) able to read and speak English, 6) willing to provide informed consent

Exclusion criteria: 1) self-reported diagnosis of lung disease including asthma, cystic fibrosis, or chronic obstructive pulmonary disease, 2) history of cardiac event or distress within the past 3 months, 3) currently pregnant (determined using urine pregnancy test), planning to become pregnant, or breastfeeding, 4) use of other tobacco products >10 days in the past month, 5) current marijuana use >10 times per month, 6) currently engaging in a vaping cessation attempt.

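### Pairwise cell comparisons at alpha 0.0017 have about 76% power with 60 completers (71% by paired t-test), not the stated 80%, if tests are two-sided and the SD is that of the paired differences

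*Combined protocol and SAP*

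**What the plan says.** Section E.i makes two power statements. For each main effect at alpha 0.01, the study "achieves 80% power to detect an effect size of 0.5 standard deviations of the paired differences". The next sentence reads "For interaction effects, we will estimate 80% power (effect size 0.5 SD) to distinguish between any two of the interaction groups", "while correcting for the pairwise tests ($p=0.01/6=0.0017". The same effect (0.5 SD) and the same power (80%) therefore appear at two alphas that differ by a factor of six.

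The inputs that E.i omits have to come from elsewhere:

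- **Sample size.** Section D.ii: "Utilizing a within-subjects, factorial design, 60 e-cig users (aged 21-25 years) will complete vaping sessions". Section D.ii.1.a (Recruitment): "Thus, we need to recruit 130 participants to have 60 complete the study".
- **Conditions.** Section D.ii: "we will prepare 8 e-liquids that differ by nicotine form, nicotine concentration, and flavor".
- **Model.** Section E: "Generalized linear mixed models will be employed to identify associations of nicotine form, nicotine concentration, and flavoring with various outcome measures", with a random participant effect. Section E.ii adds that "a fixed effect for session and a random effect for sequence will be included in all analyses".

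**The concern.** With one sample size and one standardized effect, power cannot equal 80% at both alpha 0.01 and alpha 0.0017. The two sentences agree only if 80% is a minimum, and then the stricter pairwise test is the one that has to reach it.

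Hypothesis H1c in Section A compares free-base with salt nicotine at the high concentration. That is a comparison of two form-by-concentration cells, so the pairwise figure is the one a reader would apply to it. If true power is lower than stated, a null result for H1c would be read as stronger evidence than it is.

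**Working it through.** **Inputs**

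- Completers: n = 60, each using all 8 study liquids (D.ii, D.ii.1.a).
- Effect: d = 0.5. The first sentence of E.i specifies the SD of the paired differences. I assume the same basis for the second, which says only 0.5 SD. Each form-by-concentration cell is a participant's mean over two flavors.
- Alpha: four cells give 4 × 3 / 2 = 6 pairs, and 0.01/6 = 0.00167. The plan's 0.0017 reproduces.
- Sidedness: not stated. I assume two-sided, because the sentence covers every pair of cells without direction.
- Degrees of freedom for the mixed model: 60 × 8 = 480 observations, less 60 participant, 7 session and 5 treatment terms (form, concentration, flavor, form × concentration, form × flavor) = 408. This uses a random participant intercept with common residual variance. Separate paired t-tests have 60 − 1 = 59.

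**Formula.** The non-centrality is d√n = 0.5 × √60 = 3.873. Power is the probability that a non-central t with that non-centrality exceeds the critical value. For the normal version it is Φ(3.873 − z).

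**The plan's main-effect figure, two-sided alpha 0.01**

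| Test | Critical value | Power |
|---|---|---|
| Mixed model, 408 df | 2.588 | 90.0% |
| Normal | 2.576 | Φ(1.297) = 90.3% |
| Paired t, 59 df | 2.662 | 88.2% |

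The stated 80% holds as a minimum.

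**The plan's pairwise figure, two-sided alpha 0.01/6**

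| Test | Critical value | Power | Effect for 80% at n = 60 | Completers for 80% at 0.5 SD |
|---|---|---|---|---|
| Mixed model, 408 df | 3.165 | 76.0% | 0.52 SD | 65 |
| Normal | 3.144 | Φ(0.729) = 76.7% | 0.51 SD | 64 |
| Paired t, 59 df | 3.295 | 71.4% | 0.54 SD | 69 |

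The stated 80% does not reproduce under any of the three.

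**Checks**

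- Using alpha rounded to 0.0017 gives 76.2% (408 df) and 71.7% (59 df), so rounding alpha does not close the gap. The two-sided alpha at which n = 60 and 0.5 SD give 80% is 0.0026 (408 df).
- Simulating the salt-high versus free-base-high contrast with a balanced 8 × 8 order and session effects (40,000 runs) gave 75.6% for the mixed model and 71.3% for the paired t-test.
- If the study had been sized where the main effect first reaches 80% under the mixed model (48 completers), pairwise power would be 62%.

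**The case against.** The strongest reply is that the shortfall depends on choices the plan does not make.

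- **Sidedness.** The hypotheses in Section A are directional. One-sided tests at 0.01/6 give 82.0% (mixed model), 82.6% (normal) or 78.7% (paired t). This stands as a possible reading, but nothing in Section E says tests are one-sided.
- **SD basis.** If 0.5 SD refers to a difference between two single sessions, averaging over two flavors raises paired-t power to 98% when the two flavor-specific differences are uncorrelated, falling to 79% at a correlation of 0.75. If it refers to the SD of a raw cell mean, mixed-model power depends on a within-person correlation the plan does not give: 34% at 0, 54% at 0.3, 76% at 0.5, 88% at 0.6. So other bases can help or hurt, and none is stated.
- **Partial data.** Section E.iii makes the mixed model primary, so dropouts with some sessions contribute. At the stated 20% attrition, 60 completers imply 60/0.8 = 75 starters and 15 dropouts. If those 15 attend the first 2, 3 or 4 study sessions, power is roughly 77% to 79%, 78% to 81%, or 80% to 83%, depending on the order layout and the participant variance. This could close the gap, but the attendance figures are assumptions from outside the plan.
- **Sample size.** Recruiting 130 with 20% attrition would leave 130 × 0.8 = 104, where power is about 97%. The two recruitment figures do not agree with each other, but 60 is the explicit completion target in both places.
- **Rounding.** Effects of 0.52 and 0.54 SD both round to 0.5. But 0.5 SD is given as the design effect in both sentences of E.i, and power at that value is what a reader will use.

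What remains of the objection is that the gap is small and the sentence is under-specified. It does not show that the 80% is right.

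**Conclusion.** The concern holds. On the ordinary reading of E.i (60 completers, two-sided tests, SD of the paired differences), the pairwise power is overstated by about 4 points under the planned mixed model and about 9 points by paired t-test. The chance of missing a true 0.5 SD difference between two cells is about 24% (29% by paired t-test) rather than 20%.

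Confidence is moderate because sidedness and SD basis are inferred. The 76% also assumes that a random participant intercept describes the data adequately. The main-effect statement is sound, and the design itself is not in question.

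**What to change.** Replace the two power sentences in E.i with text such as:

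> With 60 completers, two-sided tests and effects in SD of the paired differences, power at 0.5 SD is at least 88% for main effects (alpha 0.01), and about 76% under the mixed model (71% by paired t-test) for pairwise comparisons of cells (alpha 0.0017). For the latter, 80% power corresponds to about 0.52 SD (0.54 by paired t-test).

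If one-sided tests (79% to 83%), another SD basis, or a contribution from partial completers was intended, say so and give the matching figure with its assumptions. In either case, call these pairwise cell comparisons rather than interaction effects: a difference between two cells is not a test of the interaction term.

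The cost is two sentences and a slightly less favourable stated power. No extra participants are needed and conduct does not change.

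### Pairwise tests within each interaction are planned at a fixed Bonferroni cut of 0.01/6; a step-down test gives the same family-wise error with roughly 0 to 16 points more power, depending on the pattern of means

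*Combined protocol and SAP*

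**What the plan says.** Section E (Statistical Methods) sets the general level: "we will assume a significance threshold corresponding to one expected false discovery per 100 tests ($p=0.01". Section E.i (Power Analysis) then states for the interactions: "For interaction effects, we will estimate 80% power (effect size 0.5 SD) to distinguish between any two of the interaction groups", with the cut divided by six, "while correcting for the pairwise tests ($p=0.01/6=0.0017". The cells meant are "interaction groups (e.g., free base/low nic, free base/high nic" and so on: four per two-way interaction, hence six pairs.

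E.ii (Data Analytic Plan) covers the session and sequence effects but names no procedure for pairwise comparisons. No step-down, closed or gatekeeping test appears elsewhere in the document.

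**The concern.** A single-step Bonferroni cut treats each pair as if nothing had been learned from the other five. Holm's procedure tests the smallest p-value at 0.01/6, the next at 0.01/5, and so on to 0.01, stopping at the first failure. It needs no added assumption and controls the same family-wise error.

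Shaffer's version uses the logical links between pairs. Once any two of four means differ, at most three of the equalities can still be true, so the divisors become 6, 3, 3, 3, 2, 1.

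At stake is power for contrasts that rest on single pairs. H1c in Section A, free-base against salt at high concentration, is one of them. If the pairs that cross 1% and 5% nicotine are easily separated, as is plausible for plasma nicotine after the fixed 10-puff bout, a step-down test passes the unused error on to the harder form pairs. A fixed cut does not.

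**Working it through.** **Inputs.** 60 completers (D.ii: "Utilizing a within-subjects, factorial design, 60 e-cig users (aged 21-25 years) will complete vaping sessions"); a difference of 0.5 SD of the paired differences, the scale that E.i uses for main effects ("achieves 80% power to detect an effect size of 0.5 standard deviations of the paired differences"); family-wise level 0.01; six pairs. Sidedness is not stated, so two-sided is assumed and one-sided is shown as a check. The SD of the difference is taken as equal for all pairs.

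**The plan's own figures.** The cut is 0.01/6 = 0.001667, which rounds to 0.0017 and reproduces. For power, the noncentrality is 0.5 × √60 = 3.873. At the cut 0.01/6:

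- two-sided: 71.5% (paired t, 59 df), 76.7% (normal), about 75% (pooled error, 3 × 59 = 177 df);
- one-sided: 78.7% (paired t), 82.6% (normal).

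The stated 80% is therefore approached only one-sided. Two-sided, 80% needs 64 completers (normal) or 69 (paired t).

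**What each Holm step is worth.** Power of a 0.5-SD pair (two-sided paired t) at the successive cuts:

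| Divisor | 6 | 5 | 4 | 3 | 2 | 1 |
|---|---|---|---|---|---|---|
| Cut | 0.00167 | 0.0020 | 0.0025 | 0.00333 | 0.0050 | 0.0100 |
| Power | 71.5% | 73.4% | 75.8% | 78.7% | 82.5% | 88.3% |

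The ceiling on the gain is 88.3 − 71.5 = 16.8 points, reached only if the other five pairs are already rejected.

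**Gain by pattern of means.** Simulated, n = 60, paired t. Cells are ordered free-base/low, salt/low, free-base/high, salt/high, in SD units; power is for a 0.5-SD pair.

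| Pattern | Bonferroni | Holm | Gain |
|---|---|---|---|
| Crossover: 0, 0, −0.25, 0.25 | 71.4% | 71.8% | 0.4 |
| Only one cell differs, by 0.5 | 71.6% | 74.3% | 2.7 |
| Form 0.5, concentration 0.25 | 71.9% | 76.2% | 4.3 |
| Form 0.5, concentration 0.5: 0, 0.5, 0.5, 1 | 71.3% | 80.0% | 8.7 |
| Form effect at high concentration only: 0, 0, 0.5, 1 | 71.4% | 81.2% | 9.8 |
| Form 0.5, concentration 1.0: 0, 0.5, 1, 1.5 | 71.7% | 87.2% | 15.5 |
| Form 0.5, concentration 1.5: 0, 0.5, 1.5, 2 | 71.5% | 87.3% | 15.8 |

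With means 0, 0.25, 0.25, 0.5, where again only one pair reaches 0.5 SD, the gain is about 0.3 points. Shaffer adds most when few cells differ: 5.8 points over Bonferroni when one cell differs. With a pooled error term, the 2.7 to 15.8 range becomes 2.4 to 13.8.

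**Error rate.** Simulated family-wise error for Holm stayed at or below about 0.01. The slack in Bonferroni can be seen directly. With a large concentration effect and no form effect, only two of the six nulls are true, so Bonferroni spends at most 2 × 0.01/6 = 0.0033. Holm spends at most 2 × 0.01/2 = 0.01.

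**The case against.** Four points on the other side carry weight.

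- Bonferroni controls the family-wise error. A reader might infer that the planned tests are invalid or the error rate inflated. Nothing in the plan supports that; the issue is efficiency alone.
- The cut stands only in the power section. A reader might infer that the plan binds the analysis to judge every pair at 0.0017 regardless of the rest. The text does not go that far: E.ii is silent, and powering at 0.01/6 is also a normal conservative way to plan a Holm analysis, whose first step uses the same cut.
- A gain of up to 16 points needs large concentration effects, for which the documents give no figure. For puffing outcomes, Section B.2 describes compensatory puffing with low-nicotine liquids, and H1c predicts less puffing specifically with high-concentration free-base. Patterns near that (a crossover, or one cell apart) gain only about 0.4 to 3 points with Holm. Nor does the concentration argument carry over to the form-by-flavor family, whose cells do not differ in concentration; there the gain depends on the form and flavor effects.
- A reader might infer that the overall form question loses power. It does not: the salt versus free-base contrast in H1a and H1b is a main effect tested at 0.01 without division, with 88.3% power at 0.5 SD (two-sided paired t).

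All four stand and limit the size of the point. None makes Holm worse than Bonferroni as a test; at worst it gains almost nothing.

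**Conclusion.** The point holds as a cheap efficiency improvement, not as an error. The only stated pairwise rule is a valid single-step Bonferroni cut, and a step-down test at the same 0.01 never rejects less. The range of roughly 0 to 16 points assumes 60 completers, two-sided paired t tests, equal SDs of the differences, and a pattern of means that nobody yet knows. The chance of finding at least one difference is unchanged, because Holm's first step is also 0.01/6. The 0.01 covers six pairs of one interaction on one outcome, not both interactions or the whole set of outcomes.

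A reader might also take the 80% pairwise power in E.i to be simply wrong. It is not met two-sided with 60 completers under the stated cut, but sidedness is not given and one-sided calculations bracket it (78.7% to 82.6%). The supportable statement is that the margin is thin, which makes the step-down gain more useful.

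**What to change.** In E.ii, state that pairwise comparisons within each interaction use Holm's step-down test (or Shaffer's version for all pairs of four means) at family-wise 0.01, with adjusted p-values reported. Choose one of the two and fix it before analysis.

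In E.i, keep 0.01/6 as the planning cut, state the sidedness, and give the Bonferroni power as a lower bound: two-sided, about 71% by paired t or about 75% with pooled error. Tie any Holm figure to a stated pattern of means.

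The cost is a few sentences and a standard software option, with no added participants. Because step-down tests have no simple matching simultaneous intervals, show Bonferroni or unadjusted intervals alongside, labelled as such. An interval may then not agree exactly with its adjusted p-value.
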